### *Cost per Success Ratio (CPSR)*

The CPSR will be calculated to evaluate the cost per clinically successful restoration, determining the cost-effectiveness of each material in achieving successful outcomes, defined as restorations that will show no failure after 12 months. The CPSR will be calculated using the following formula:

$$CPSR = \frac{\text{Total Cost}}{\text{Number of Successes}}$$

Where:

- Total Cost refers to the overall cost per patient for each material,

- Number of Successes refers to the number of restorations that met the pre-defined criteria for clinical success (i.e., clinically excellent rate after 12 months).

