## 12. Outcomes

Outcomes will be assessed by mouth mirror, dental explorer, standardized photographs and FDI probe according to modified USPHS criteria and Revised FDI criteria for direct and indirect restorations:

- **Primary outcomes:** All restorations will be assessed for functional, biological, and aesthetic properties using Revised FDI criteria for direct and indirect restorations. They will be given a score (clinically excellent/very good, clinically good, clinically satisfactory, clinically unsatisfactory, clinically poor).
- **Secondary outcomes:** Cost-Effectiveness Analysis

Cost-effectiveness will be assessed by calculating the Incremental Cost-Effectiveness Ratio (ICER) and the Cost per Success Ratio (CPSR). These metrics will be used to compare the cost and clinical outcomes of LS-GRC and RMGI in treating class V cavities.

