### *Incremental Cost-Effectiveness Ratio (ICER)*

The ICER will be used to compare the cost-effectiveness of LS-GRC versus RMGI by evaluating the additional cost for each successful outcome provided by LS-GRC compared to RMGI. The ICER will be calculated using the following formula:

$$ICER = \frac{(C_2 - C_1)}{(E_2 - E_1)}$$

Where:

- $C_2$  and  $C_1$  are the total costs of LS-GRC and RMGI, respectively,
- $E_2$  and  $E_1$  are the respective effective outcomes (i.e., clinically excellent rates after 12 months).

The cost calculation methodology will account for several key factors, including the material cost per restoration, clinical application costs, and replacement or repair costs over time. Additionally, indirect costs, such as patient time, transportation, and the number of follow-up visits, will also be considered.

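### The cost per success ratio is an average within each arm, so using it to compare the materials makes their order depend on shared costs and on a threshold nobody chose

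*Combined protocol and SAP*

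**What the plan says.** In the combined protocol and SAP, section 12 (Outcomes) makes cost-effectiveness the only secondary outcome and gives it two metrics, the ICER and the CPSR. Of both together it says: "These metrics will be used to compare the cost and clinical outcomes of LS-GRC and RMGI in treating class V cavities".

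The ICER subsection divides the difference in cost by the difference in the proportion rated clinically excellent at 12 months. The two cost terms "are the total costs of LS-GRC and RMGI, respectively". The costs to be counted are described there as "including the material cost per restoration, clinical application costs, and replacement or repair costs over time", followed by: "Additionally, indirect costs, such as patient time, transportation, and the number of follow-up visits, will also be considered".

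The CPSR subsection divides total cost by the number of successes. It opens: "The CPSR will be calculated to evaluate the cost per clinically successful restoration, determining the cost-effectiveness of each material in achieving successful outcomes". Its numerator is an overall cost, not an incremental one: "Total Cost refers to the overall cost per patient for each material".

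The documents give no cost amounts, no value for an extra success, no rule for costs that are the same in both arms, and no statement of which metric prevails if the two point different ways. The statistical methods in section 20 cover categorical data only and say nothing about cost data.

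**The concern.** The two materials are alternatives for the same tooth. Choosing between them turns on what the dearer one adds in cost and what it adds in success. The CPSR answers a different question: what a success costs on average within one arm.

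If the lower CPSR is taken to mark the more cost-effective material, two things follow. First, costs that do not depend on the choice of material still enter the comparison. Second, the comparison quietly fixes a price for an extra success, namely whatever the other material happens to cost per success.

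Shared costs are plausible here. Cavity preparation, with anaesthesia and rubber dam, is described once for both groups (Restorative procedures), and there is one follow-up schedule for both. At stake is the economic conclusion: the same trial data could be reported in favour of either material, depending on which shared items are counted and how they are valued.

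**Working it through.** **Inputs.** The plan gives no cost or CPSR figure to reproduce, so all costs below are assumptions in arbitrary units. The success rates come from section 14: 68.7% for RMGI, and 98.7% if the 30-point difference is upward. The upward reading fits the plan: a two-sided 5% z test with 80% power for 68.7% v 98.7% (pooled variance, no continuity correction) gives 23 per group, as stated, whereas 38.7% would give 43. The 68.7% is a marginal-discoloration success rate from a cited study, not a 12-month clinically excellent rate. It serves only as an illustration.

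**Notation.** E1 and m1 are the success rate and arm-specific cost of RMGI; E2 and m2 are those of giomer; k is the cost common to both arms.

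- CPSR of RMGI = (k + m1)/E1; CPSR of giomer = (k + m2)/E2
- ICER = [(k + m2) − (k + m1)]/(E2 − E1) = (m2 − m1)/(E2 − E1), so k cancels

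**Step 1: what ranking by CPSR implies.** For E2 > E1:

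(k + m2)/E2 < (k + m1)/E1
⇔ E1(m2 − m1) < (E2 − E1)(k + m1)
⇔ ICER < CPSR of RMGI.

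The order flips at k* = (m2·E1 − m1·E2)/(E2 − E1). This is positive only if m2/m1 > E2/E1. The result is symmetric if RMGI is the dearer and more effective material.

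**Step 2: example with m1 = 100, m2 = 150, E1 = 0.687, E2 = 0.987.**

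ICER = 50/0.300 = 166.7 at every k.
k* = (150 × 0.687 − 100 × 0.987)/0.300 = (103.05 − 98.70)/0.300 = 14.5.

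| Common cost k | CPSR RMGI | CPSR giomer | Lower CPSR | ICER |
|---|---|---|---|---|
| 0 | 100/0.687 = 145.6 | 150/0.987 = 152.0 | RMGI | 166.7 |
| 50 | 150/0.687 = 218.3 | 200/0.987 = 202.6 | giomer | 166.7 |

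**Step 3: when it cannot happen.** At these rates E2/E1 = 0.987/0.687 = 1.44. If giomer's arm-specific cost is below about 1.44 times RMGI's, k* is negative and no shared cost changes the order. For m2 = 140, k* = (96.18 − 98.70)/0.300 = −8.4, and giomer has the lower CPSR throughout. If one material is both cheaper and more effective, k* is also negative, and the CPSR and the incremental comparison agree.

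**Step 4: range of the flip point (m1 = 100, E1 = 0.687).**

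| Gain in success | Giomer's extra arm-specific cost | k* |
|---|---|---|
| 5 points | 10% to 100% | 37 to 1274 |
| 10 points | 20% to 100% | 37 to 587 |
| 10 points | 10% | −31 (no reversal) |
| 30 points | 50% to 100% | 15 to 129 |
| 30 points | 10% to 30% | below 0 (no reversal) |

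For example, with a 10-point gain and m2 = 130, the ICER is 30/0.100 = 300 at every k. The CPSRs are 145.6 v 165.2 at k = 0 (RMGI lower) and 436.7 v 419.3 at k = 200 (giomer lower).

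**Step 5: disagreement with an incremental decision.** Let λ be the value placed on one extra success. The incremental net benefit of giomer in the step 2 example is λ × 0.300 − 50.

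- λ = 150: 45 − 50 = −5, so giomer is rejected. At k = 50 the CPSR favours giomer.
- λ = 200: 60 − 50 = +10, so giomer is accepted. At k = 0 the CPSR favours RMGI.

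**Step 6: the formula as literally written.** Dividing a per-patient cost by a count of successes, with 28 teeth in each arm, only divides both CPSRs by 28. They become 5.20 v 5.43 at k = 0 and 7.80 v 7.24 at k = 50, so the flip point is unchanged. Correcting the units would not remove the problem.

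**The case against.** A reader might infer that the CPSR contradicts the ICER, or that it can name the wrong material. The documents do not support that. When one material costs more and works better, an ICER ranks nothing until someone says what an extra success is worth, and the plan states no such value. At an ICER of 166.7 neither material is right or wrong in itself. What stands is narrower: the CPSR order can disagree with the incremental decision at a given value per success, and it can change when that decision does not.

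It is also fair to say that no sentence announces a ranking by CPSR, and that the cost-effectiveness of each material could be read as a within-arm description. But section 12 says in terms that both metrics will be used to compare the materials, so the between-arm use is written into the plan.

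The shared costs are partly an inference. Anaesthesia, rubber dam and cavity preparation are not named as cost items. The cost list stands under the ICER, and its use in the CPSR rests on the reference to overall cost. Chair time may differ because the application steps differ, and failures may bring extra visits (sections 22 and 30). Patient time, transportation and visits are already promised, so including them is not wholly discretionary. Even so, whatever part is equal across arms enters the CPSR and not the ICER, and neither its amount nor its valuation is fixed.

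Finally, the example costs were chosen to show a reversal, and the cost ratio of 1.5 lies just above the 1.44 boundary. That is why the no-reversal cases are set out above.

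**Conclusion.** The point holds. The plan uses an average ratio to compare two alternatives, and when the more effective material costs more, the order it gives rests on an implicit threshold equal to the other material's own cost per success. That threshold rises with every shared cost counted. The order can therefore reverse with incremental cost and effect unchanged. The algebra is exact and does not depend on the illustrative figures.

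The numerical size is a demonstration of possibility, not a forecast: a flip at a shared cost of about 15 for assumed costs of 100 and 150 and rates of 68.7% and 98.7%. Nothing in the documents shows that a reversal is likely, and they neither establish nor exclude the conditions for one. The consequence is confined to the secondary outcome. The ICER, the primary outcome and the sample size are untouched. The change is worth making before the costs are analysed, because the plan leaves open which metric would carry the conclusion.

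**What to change.** Three edits to section 12:

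1. In the opening sentence of the CPSR subsection, delete the clause that has the ratio settle each material's cost-effectiveness. State that the CPSR is a description within each arm and is not compared between arms.
2. In the paragraph introducing the secondary outcome, state that the comparison rests on incremental cost and incremental effect. Present it as the ICER or as net monetary benefit over a stated range of values per extra success, with uncertainty. The range matters: without it, incremental cost and effect give no order when one material is both dearer and more effective.
3. In the cost description, list costs common to both arms on a separate line, so that a reader can see what cancels.

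This needs some rewording and a choice of value range, but no new data, provided costs are recorded per patient as the CPSR numerator implies. The downside is losing a simple headline ratio for ranking the materials.

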### 14. Sample size calculation:

The sample size was calculated based on a previous study by *Vural et al in 2021*, in which percentage of successful class V restorations (Score A and B) using resin modified glass ionomer regarding marginal discoloration was 68.7%. By implementing a two tailed Z test for difference between two independent proportions with an alpha level of 5% and a power of 80%. The minimum sample size needed was 23 per group in order to detect a difference of 30%. Sample size was increased by 20% to compensate for possible dropouts to reach 28 teeth per group. Sample size was performed using G\*Power version 3.1.9.2 for windows.

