## **30. Post-trial care**

Patients will be followed up after restoration to ensure oral hygiene measures. When there is any evidence of restoration failure, patients will be treated by immediate restoration removal and glass ionomer restoration will be placed.

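### The Cost per Success Ratio has two conflicting definitions of success and divides a per-patient cost by a count of restorations

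*Combined protocol and SAP*

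**What the plan says.** Cost-effectiveness is the only secondary outcome, and it consists of two metrics, the ICER and the CPSR (section 12 and section 20b).

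The CPSR text gives its purpose as "to evaluate the cost per clinically successful restoration". It then describes successful outcomes as "defined as restorations that will show no failure after 12 months". The formula divides Total Cost by Number of Successes, with this key:

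- Numerator: "Total Cost refers to the overall cost per patient for each material".
- Denominator: "Number of Successes refers to the number of restorations that met the pre-defined criteria for clinical success (i.e., clinically excellent rate after 12 months".

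The grading scale, also in section 12, has five levels: "clinically excellent/very good, clinically good, clinically satisfactory, clinically unsatisfactory, clinically poor". The ICER names a single effect measure; its E terms "are the respective effective outcomes (i.e., clinically excellent rates after 12 months".

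**The concern.** There are two separate problems.

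**Success is defined twice.** A restoration graded good or satisfactory at 12 months is not clinically excellent, so the denominator leaves it out. Nothing in the plan calls such a restoration a failure, so the opening sentence would count it. Failure is not mapped to an FDI grade anywhere. Section 30 uses the word for restorations that are taken out ("When there is any evidence of restoration failure, patients will be treated by immediate restoration removal"), which does not fit a reading in which everything below excellent has failed. That section is cited only for how it uses the word.

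**The units do not match.** A cost for one patient is divided by a count over a whole arm, so the result depends on how many restorations were evaluable as well as on cost and success.

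The material that appears cheaper per success can depend on either choice. If both stay open, the definition could be settled after the grades are known.

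**Working it through.** **The plan's own figures.** No CPSR value is stated, so there is none to reproduce. The only stated figures that enter the scaling are the group sizes in section 14: "The minimum sample size needed was 23 per group", raised by 20% for dropout. A two-sided pooled z test of 68.7% vs 98.7% at 5% alpha and 80% power gives 23, and 23 × 1.2 = 27.6, rounded up to 28. Both figures reproduce.

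**Assumptions.** All costs and outcome counts below are illustrative. One restoration per patient is assumed; this fits section 14 (28 teeth per group) and section 16a (participants numbered 1 to 56, and 2 × 28 = 56).

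**Notation.** c = cost per patient, n = restorations in the arm, S = successes, p = S/n.

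*Step 1: units.* Two forms are coherent, and they are equal: arm total cost / successes = nc/S, and cost per patient / success proportion = c/p = nc/S. The literal formula is c/S = c/(np), which is too small by the factor n. With c = 100 and 25 of 28 successes:

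- literal: 100/25 = 4.0
- coherent: 2,800/25 = 100/(25/28) = 112.0

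*Step 2: effect of unequal evaluable numbers.* Take the same cost (100) and the same 90% success in both arms, so the true gap is zero. The literal formula gives:

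- 28 vs 28: 100/25.2 = 3.97 in both arms, no gap
- 28 vs 26: 3.97 vs 100/23.4 = 4.27, gap 28/26 = 1.077 (8%)
- 28 vs 23: 3.97 vs 100/20.7 = 4.83, gap 28/23 = 1.217 (22%)

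The ranking can also reverse. With giomer at cost 115 and 25/28 successes, and RMGI at cost 100 and 21/23:

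- literal: 115/25 = 4.60 vs 100/21 = 4.76, giomer cheaper
- coherent: 115/(25/28) = 128.8 vs 100/(21/23) = 109.5, RMGI cheaper

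*Step 3: effect of the success definition.* This uses the coherent form, 28 per arm, with giomer at 120 and RMGI at 100. Each pair is giomer vs RMGI.

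| Case | No failure (S) | Excellent (S) | CPSR, no failure | CPSR, excellent |
|---|---|---|---|---|
| (a) | 27 vs 26 | 24 vs 16 | 124.4 vs 107.7 | 140.0 vs 175.0 |
| (b) | 27 vs 27 | 22 vs 18 | 124.4 vs 103.7 | 152.7 vs 155.6 |
| (c) | 27 vs 26 | 21 vs 20 | 124.4 vs 107.7 | 160.0 vs 140.0 |

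For example, in (a): 120/(27/28) = 124.4 and 100/(26/28) = 107.7; 120/(24/28) = 140.0 and 100/(16/28) = 175.0. RMGI is cheaper under no failure in all three cases. Under excellent, giomer is cheaper in (a) and (b), and RMGI stays cheaper in (c).

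With equal n, giomer is cheaper per success when its cost ratio to RMGI is below the ratio of success counts. The definitions therefore disagree on ranking when the cost ratio lies between the two success ratios:

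- (a) 27/26 = 1.04 to 24/16 = 1.50
- (b) 27/27 = 1.00 to 22/18 = 1.22
- (c) 27/26 = 1.04 to 21/20 = 1.05

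The assumed cost ratio of 1.20 falls inside the first two ranges and outside the third. Within the RMGI arm of (a), the definition alone moves the CPSR by 175.0/107.7 = 1.625, an increase of 62.5%.

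**The case against.** The strongest reply is that the intention can be recovered. Both formula keys, for the ICER and for the CPSR, use clinically excellent, so failure might mean not meeting that criterion. The label Total Cost, the word rate and the stated purpose all point to a coherent ratio, and an analyst would notice a cost per success of 4.0 when one restoration costs 100. With equal evaluable numbers the arm-size factor cancels from the between-material ratio. The 28 vs 23 case puts all losses in one arm, and 23 is a minimum sample size, not a forecast of loss. The cost and outcome figures are hypothetical.

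Part of this stands. The text does lean towards clinically excellent, the unit fault alone would be a modest wording correction, and the figures show what can happen, not what is likely. But reading good and satisfactory as failures is strained, and the opening sentence is still a definition that contradicts the key. Total Cost is expressly defined per patient. Evaluable numbers need not stay equal: section 14 allows for dropout and section 20c plans no imputation unless otherwise specified. The statistical methods in section 20a say nothing about the CPSR that would settle either point.

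Two further remarks are fair and bear on the fix. The FDI assessment covers functional, biological and aesthetic properties, so naming a grade also requires saying which properties count and how they are combined. The ICER has one effect measure, but it does not say whether its total costs are per arm or per patient.

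**Conclusion.** The concern holds. As written, the CPSR has two definitions of success that agree only if every restoration below the top grade is a failure, which the plan does not say. Followed literally, its formula gives the cost per successful restoration divided by the arm size, a factor of 28 at the planned numbers.

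The choice of definition can reverse the ranking of the materials even with equal arms, though it need not. The unit fault only rescales both arms when evaluable numbers are equal, but it distorts the comparison when they differ. The arm-size factor, and the equality of the two coherent forms, rest on one restoration per patient.

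This should be fixed before analysis. It concerns one of the two metrics in the only secondary outcome and leaves the primary outcome, the sample size and the ICER effect measure untouched.

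**What to change.** Amend section 12 before analysis:

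- Define the CPSR as mean cost per patient / success proportion, or equivalently arm total cost / number of successes. State that each patient contributes one restoration; if that is not so, put cost and success on a per-restoration basis.
- Compute numerator and denominator on the same stated set of patients, and say how restorations without a 12-month grade are counted.
- Reconcile the two success definitions into one, named by FDI grade or grades, with the properties that count and the rule for combining them. Keep it consistent with the ICER effect measure, and state the ICER cost basis at the same time. If the other definition is also reported, label it a sensitivity analysis.

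The cost is a few sentences, with slightly more analysis if the second definition is reported. No new data are needed.

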**c) Handing of missing data:**

All randomized participants will be included in the primary analysis according to the intention per protocol analysis. Participants who discontinue or are lost to follow-up will be analyzed in the groups to which they were originally assigned, regardless of adherence to the intervention. No imputation will be performed for missing outcome data unless otherwise specified.

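### As written, the cost per success ratio (CPSR) divides a per-patient cost by a count of 12-month successes, so it depends on how many restorations are retained and can treat losses differently from the ICER

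*Combined protocol and SAP*

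**What the plan says.** All references are to the combined protocol and SAP.

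- **Section 12, CPSR.** The formula is total cost over number of successes. For the numerator, "Total Cost refers to the overall cost per patient for each material". For the denominator, "Number of Successes refers to the number of restorations that met the pre-defined criteria for clinical success", followed in the same line by the gloss "i.e., clinically excellent rate after 12 months". The opening sentence describes success differently: "defined as restorations that will show no failure after 12 months".
- **Section 12, ICER.** The effect terms "are the respective effective outcomes (i.e., clinically excellent rates after 12 months". The section does not say whether the rate is taken over all randomized or over those assessed. Its cost list covers material, application, and replacement or repair costs, plus patient time, transport and follow-up visits.
- **Section 20(c), missing data.** "All randomized participants will be included in the primary analysis according to the intention per protocol analysis" and "No imputation will be performed for missing outcome data unless otherwise specified". Nothing in section 12 specifies otherwise for the cost metrics.
- **Section 14, sample size.** The minimum is 23 per group, and "Sample size was increased by 20% to compensate for possible dropouts to reach 28 teeth per group".

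**The concern.** A restoration that is not seen at 12 months cannot be shown to meet a 12-month criterion. With no imputation it can never enter a count of successes, yet its material and application costs were incurred at placement. A count-based CPSR therefore treats each loss as a failure. The arm that loses more patients looks less cost-effective even if its restorations perform equally well.

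The ICER uses a rate with no stated denominator. If the rate is taken among those assessed, losses drop out of the ICER but act as failures in the CPSR. The two metrics make up the trial's only secondary outcome, and on the same data they could point in different directions because of who returned and not because of how the materials performed.

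**Working it through.** **Inputs.** From section 14: 23 per group minimum, 28 per group after the dropout increase, control success 68.7%, difference 30 points (so 98.7% in the other arm if the difference is upward). The documents give no costs, so I assume the same cost C per restoration in both arms.

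**The plan's own figures.** A two-sided pooled Z test of 68.7% v 98.7% at 5% alpha and 80% power gives 23 per group (power 80.8%). Then 23 × 1.2 = 27.6, rounded up to 28. Both stated figures reproduce. An arm of 28 can lose 5 (5/28 = 17.9%) before it falls below 23; a 20% loss leaves 22.4.

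**Effect of attrition on the count.** With true success rate p and m restorations retained, the expected count is p × m. Using the arm's total cost:

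CPSR = 28C / (p × m)

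With the literal per-patient cost it is C / (p × m). The ratio between two arms with equal p is the ratio of retained numbers either way. At p = 0.687:

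| Lost (arm 1 v arm 2) | Retained | CPSR, arm 1 v arm 2 | Ratio |
|---|---|---|---|
| 0 v 0 | 28 v 28 | 1.456C v 1.456C | 1.00 |
| 5 v 5 | 23 v 23 | 1.772C v 1.772C | 1.00 (both up by 28/23 = 1.217) |
| 5 v 6 | 23 v 22 | 1.772C v 1.853C | 1.045 |
| 0 v 5 | 28 v 23 | 1.456C v 1.772C | 1.217 |
| 3 v 8 | 25 v 20 | 1.630C v 2.038C | 1.25 |

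A rate-based CPSR, C/p, is 1.456C in every row.

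**How often losses differ by chance.** Let retained numbers be Binomial(28, 0.8) in each arm, independently. The arms then lose different numbers in 87% of trials, and differ by 3 or more in 40%. For identical materials the retained counts alone put the CPSRs at least 10% apart in 45% of trials and at least 20% apart in 19%. At 10% loss these are 26% and 5%.

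**Reversal example.** One arm has 20 successes of 23 seen (87.0%); the other has 21 of 28 (75.0%).

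- Count-based: 28C/20 = 1.400C v 28C/21 = 1.333C. The arm with the better rate looks worse.
- Rate-based: C/0.870 = 1.150C v C/0.750 = 1.333C.
- With the 5 losses counted as failures, the first arm is at 1.400C. Counted as successes, 28C/25 = 1.120C. The range spans the other arm's 1.333C, so the ranking depends on the losses.

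**How often the count ranks the arms strictly against their completer rates** (simulation, 20% loss in both arms):

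| True success rates | Trials reversed |
|---|---|
| 68.7% v 68.7% | 14% |
| 90% v 90% | 20% |
| 80% v 90% | 14% |
| 68.7% v 98.7% (design difference) | 1.7% |

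**The case against.** **The denominator may be meant as a rate.** The gloss in the CPSR line says so, and a per-patient cost makes sense only over a rate. On that reading the attrition effect need not arise. This stands as a reading of intent. But the printed formula, its label and its definition all say count, and an analyst who follows them gets the table above.

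**A reader might infer that the plan scores losses as failures in the CPSR and excludes them from the ICER.** The documents do not support that as fact. The ICER section states no denominator, and the missing-data section includes all randomized participants (in the primary analysis) while barring imputation. With 28 as the ICER denominator, both metrics would treat losses as failures and agree. What can be said is that the two metrics can diverge, because no shared rule is given.

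**A reader might also infer that the 20% dropout allowance itself distorts the comparison.** It does not: equal loss scales both CPSRs by the same factor, and only a difference in loss separates the arms. The 20% is also a sample-size increase, which covers a 17.9% loss.

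**Costs do not all stay fixed.** Repair, travel and visit costs accrue over follow-up and go partly unrecorded for lost patients. If cost were totalled only over those followed, a count would show no attrition effect. That is correct, but the plan does not specify that basis.

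**The size should not be overstated.** Two of the four reversal scenarios have no true ranking to reverse. Sampling noise also remains after the fix: with 68.7% in both arms and 20% loss, a rate-based CPSR still differs by at least 10% in 64% of trials, against 69% for the count. At 90% in both arms the gain is larger, 35% against 61%. The metric is secondary and no test of it is planned.

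**Conclusion.** Wrong as written. The CPSR paragraph contradicts itself on count or rate, on no failure or clinically excellent, and on a per-patient cost set over an arm-level count. Taken literally, the formula makes the result depend on retention: a 25% gap between identical materials at 3 v 8 lost, and 22% inflation of both arms, with no change of ranking, at 5 v 5. These figures assume 28 per arm, equal unit cost and placement costs that stay in the numerator. The simulated frequencies also assume loss that is independent of outcome. Reversal of ranking is mainly a risk when the materials perform similarly; at the plan's own design difference it occurs in about 2% of trials. That the CPSR and the ICER disagree on losses is a possibility the text leaves open, not something it states.

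**What to change.** In section 12, define CPSR = mean cost per restoration / proportion successful at 12 months. State with it:

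1. One definition of success, replacing the two now given.
2. One analysis set for cost and success alike, used in both the CPSR and the ICER: restorations with known 12-month status, with any that failed earlier counted as known failures.
3. How this set fits with the all-randomized wording in section 20(c), whose label mixes intention-to-treat and per-protocol and needs correcting at the same time.
4. Two sensitivity lines for both metrics: all lost restorations counted as failures, and all counted as successes.

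The cost is a few sentences and a re-tabulation of data already collected, with no extra patients or visits. The downside is that the main figure assumes lost restorations resemble those seen; the two sensitivity lines bound how far that matters.
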